7.3 Subject Population(s) for Analysis

Subject population for analysis will include any subject enrolled in the study who received at least two weeks of treatment with study eye drops and attended at least the first post-treatment (week 2) follow up visit.

8 Safety and Adverse Events

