Net	Neutrophil extracellular trap
OSDI	Ocular Surface Disease Index
Otc	Over the counter
QID	Four times per day
rhDNase1	Recombinant human deoxyribonuclease I
SAE	Serious Adverse Event
SGL	Subject Global Assessment
SP	Substance P
UIC	University of Illinois at Chicago
VA	Visual Acuity
VAS	Visual Analog Scale

Study Summary

Title	A Phase I/II Randomized Placebo-Controlled, Double-Blind Single-Center, tolerability and preliminary efficacy clinical trial of recombinant human deoxyribonuclease (rhDNase) eye drops in patients with dry eye disease.
Short Title	DNase treatment for dry eyes
Protocol Number	UIC-CNBL-1001
Phase	Phase I/II
Methodology	Double-blind
Study Duration	10 weeks
Study Center(s)	Single-center
Objectives	To evaluate the tolerability and preliminary efficacy of rhDNase1 eye drops in patients with Dry Eye Disease.
Number of Subjects	72 (study drug at least 30, placebo at least 30)
Diagnosis and Main Inclusion Criteria	Men and women ≥ 18 years of age with a diagnosis of established Dry Eye Disease, with Schirmer I < 10 , Ocular surface staining ≥ 1 and OSDI mild (≥ 13).
Study Product, Dose, Route, Regimen	Study drug: rhDNase1 (Pulmozyme®), 0.1% eye drops four times a day for eight weeks. Control: drug vehicle eye drops four times a day for eight weeks.
Duration of administration	8 weeks
Reference therapy	None
Statistical Methodology	Descriptive statistics will be used for all primary and safety endpoints, when appropriate. A Wilcoxon test will be used to compare changes in subjective symptoms from Baseline to follow-up values at 2 weeks, 4 weeks, 6 weeks, 8 weeks and 10 weeks. Primary efficacy measure is the change in the OSDI reported between Baseline and Week 8. Primary safety measure is the proportion of patients at week 8 who were able to successfully complete a full eight weeks of therapy with topical administration four times per day (q.i.d).

1 Introduction

This document is a protocol for a human research study. This study is to be conducted according to US and international standards of Good Clinical Practice (FDA Title 21 part 312 and International Conference on Harmonization guidelines), applicable government regulations and Institutional research policies and procedures.

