Participants randomized to the placebo have a risk of worsening dry eye disease. All study subjects will be encouraged to contact the research team immediately if they experience worsening of their DED.

No psychological, social, legal, or financial risk is expected from participating in the research.

There is always a risk of a loss of confidentiality.

2 Study Objectives

The objective of this study is to establish whether patients with Dry Eye Disease are able to tolerate receiving rhDNase1 0.1% eye drops four times a day for eight weeks (primary tolerability objective) and to investigate the preliminary efficacy of rhDNase1 topical eye drop solution 0.1% in treating Dry Eye Disease (primary efficacy objective).

3 Study Design

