3.4 Primary Safety Endpoints

Safety assessments include Vital Signs, recording of all complications and adverse events, as well as ophthalmic exam findings. All ocular and non-ocular adverse events will be assessed for severity and relationship to the investigational product.

Primary safety endpoint:

- The proportion of subjects at week 8 who were able to successfully complete a full eight weeks of therapy with topical administration four times per day (q.i.d.)

Secondary safety endpoint:

- All adverse events reported, whether deemed related to treatment, or not.
- Clinically significant changes in vital signs or ophthalmic examination from baseline.

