The subjects will be monitored frequently (at 2 weekly intervals) to ensure that they are not subjected to any undue risks during the wash out period or during the course of the study. Additionally, they will be warned of the possible signs and symptoms of clinical worsening of DED, and advised to contact the research team immediately in case any of those symptoms occur. Subjects will also be encouraged to contact the research team in case they experience any ocular discomfort during the wash out period or during the course of the study. The subject's condition will be monitored by the physician (Principal Investigator) at each study visit, as well as at any interim visit (in case of adverse symptoms, as mentioned above). Any worsening of DED or any adverse event due to the study drug will be recorded. In case of clinical worsening, based on the individual subject's clinical condition, one or more of the following therapeutic decisions may be implemented: (1) Increasing the frequency of use of artificial tears, (2) Re-starting the use of anti-inflammatory therapy (Restasis/ corticosteroids), (3) Withdrawal of the use of study drug (if worsening occurs during the course of the study). The decision will be made by the physician (Principal Investigator) based his clinical judgment as per the individual subject's clinical condition. If additional anti-inflammatory therapy (Restasis/ corticosteroids) is instituted during the wash-out period, the subject will be excluded from the study. Also, if additional anti-inflammatory therapy (Restasis/ corticosteroids) is instituted during the course of the study and/or the study drug is

withdrawn, the subject will be excluded from the study. After any clinical worsening is noted, the subjects will be followed more closely (weekly) until complete resolution of symptoms and return to the subject's previous baseline.

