5.7 Rescue Plan

The research staff, including the PI, will be masked to randomization, thus will not be aware if a particular subject receives study drug or placebo. Subjects will be monitored by the Principal Investigator at each study visit. Any worsening of DED or any adverse event (AEs) will be recorded and in the case of AEs followed to resolution. In case of clinical worsening/ adverse event(s), based on the individual subject's clinical condition, one or more of the following therapeutic decisions may be implemented:

- (1) Increasing the frequency of artificial tears use,
- (2) Re-starting the use of anti-inflammatory therapy (Restasis/ corticosteroids),
- (3) Discontinue the study drug.

The decision will be made by the Principal Investigator based on his clinical judgment and the individual subject's clinical condition. If additional anti-inflammatory therapy (Restasis/ corticosteroids) is instituted and/or the study drug is discontinued, the subject will be withdrawn from the study. If an adverse event is severe enough to discontinue the subject from the study, the PI may decide to break the subject's randomization code if it seems relevant to the treatment of his/her ocular condition at that time. He/ She will receive the treatment required for his/ her eye condition as per established clinical guidelines.

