7.1 Sample Size Determination

Our intention is to have at least 30 subjects in each group (study drug/ vehicle) complete the study. This number is based on published reports of similar randomized clinical trials designed to determine

efficacy and tolerability of a test drug in Dry Eye Disease.³²⁻³⁴ A total of 72 subjects will be enrolled so that even if 20% of subjects are unable to complete the study, we will still remain with the intended number of subjects who complete the study (at least 30 subjects in each group). Subjects will be randomized to either of the two groups (#1, placebo; #2, study drug) as explained in section 5.3. However, all subjects who received at least two weeks of treatment with study eye drops and attended at least the first post-treatment (week 2) follow up visit will be included for analysis.

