7.2 Statistical Methods

Descriptive statistics will be used for all primary and secondary endpoints, when appropriate.

We will define outcome measures on the basis of the change for each subject from baseline to each follow-up point, controlling for chance imbalances in the mean baseline values between treatment groups. A Wilcoxon Signed-rank test will be used for paired comparison of quantitative variables (OSDI score) between the baseline and each post-baseline time points. Chi-square test will be used to compare qualitative variables (Investigator's rating scale/ changes in concomitant medications) between the 2 groups. Two-sided $P < .05$ will be considered statistically significant for all comparisons. 95% Confidence interval will be provided for comparison between the investigational drug and placebo for the primary efficacy, the primary safety, and the secondary endpoints.

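### The only analysis set the plan defines (two weeks of treatment plus the week 2 visit) would, if applied to the eight-week completion endpoint, drop early stoppers who are certain non-completers.

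*Combined protocol and SAP*

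**What the plan says.** Section 7.3 gives one population for analysis: "any subject enrolled in the study who received at least two weeks of treatment with study eye drops and attended at least the first" follow-up visit, at week 2. Section 7.1 states the same rule, for "all subjects who received at least two weeks of treatment with study eye drops" who also attended that visit. No all-randomised, all-dosed or safety set is defined, and no endpoint is exempted.

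The primary safety endpoint in section 3.4 is "The proportion of subjects at week 8 who were able to successfully complete a full eight weeks of therapy" at four doses a day. The Study Summary agrees: "Primary safety measure is the proportion of patients at week 8 who were able to successfully complete a full eight weeks of therapy". Neither place names a denominator. The endpoint serves the objective in section 2, whether patients are "able to tolerate receiving rhDNase1 0.1% eye drops four times a day for eight weeks (primary tolerability objective"). Section 7.2 promises a 95% confidence interval for the "comparison between the investigational drug and placebo for the primary efficacy, the primary safety, and the secondary endpoints".

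Three other provisions touch the same subjects:
- Section 5.6 says that if anti-inflammatory therapy is started or the drug is "withdrawn, the subject will be excluded from the study". Section 5.7 says that if such therapy is "instituted and/or the study drug is discontinued, the subject will be withdrawn from the study".
- Section 8.1 allows a subject who withdraws for an adverse event to be replaced.
- Section 8.6 has adverse events evaluated in everyone exposed to study drug. Sections 8.4 and 8.5 record whether an event led to stopping the drug or leaving the study.

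**The concern.** A completion endpoint is informative because of the people who fail it. Someone who stops on day 3 has failed it for certain. A set that requires two weeks of treatment takes that person out of the denominator and nobody out of the numerator, so the reported proportion drifts towards the favourable answer on the trial's primary tolerability question. Section 1.5 names burning or irritation as the most likely discomforts, and section 1.4 reports no published use of the drug as eye drops, so stopping in the first days is foreseeable even though no rate is given.

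The comparison between arms is at risk as well, but mainly if early stopping is unequal. VAS tolerability and the efficacy endpoints would be restricted by the same post-randomisation event, so the arms would no longer be compared as randomised.

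**Working it through.** **Inputs from the documents.** 72 enrolled, at least 30 completers intended per group, and 20% non-completion allowed for (7.1). Treatment lasts 8 weeks and the set requires 2 of them (5.2, 7.3). Each visit dispenses 56 droppers, used at 4 a day (5.4, 5.8).

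**Assumptions.** The number and timing of early stops are not given, so every count below is assumed. Arms of 36 are also assumed: section 5.3 describes no blocking, so equal arms are not assured.

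**The plan's own figure.** No completion rate is stated. The nearest figure is the enrolment of 72, which 60 x 1.20 reproduces, whereas 72 x 0.80 = 57.6 falls short of 60. That is a separate matter; only the 20% is borrowed here. 0.20 x 36 = 7.2, taken as 7 non-completers per arm.

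**Formula.** With N dosed, C completers and E non-completers who stop before week 2, completion is C/N in all dosed subjects and C/(N - E) in the 7.3 set. If C > 0 and E > 0, the second is always larger.

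**One arm, 7 non-completers (Wilson 95% CI).**
- All dosed: 29/36 = 80.6% (65.0 to 90.2).
- 2 stop early: 29/34 = 85.3% (69.9 to 93.6). Stops spread evenly over eight weeks give 7 x 2/8 = 1.75, about 2.
- 4 stop early: 29/32 = 90.6% (75.8 to 96.8).

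Arm size matters little at even timing: 24/30 = 80.0% becomes 24/28 = 85.7%, and 34/42 = 81.0% becomes 34/40 = 85.0%.

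**The attendance condition.** It can remove a subject who is still on drops. One eventual completer who misses only week 2 moves 29/36 = 80.6% to 28/35 = 80.0%. This is probably rare, because the supply lasts 56/4 = 14 days.

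**Two arms, 10 drug and 4 placebo non-completers, 36 per arm (Newcombe 95% CI).**

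| Early stops, drug v placebo | Drug | Placebo | Difference, points (95% CI) |
|---|---|---|---|
| None removed | 26/36 = 72.2% | 32/36 = 88.9% | -16.7 (-34.2 to 1.9) |
| 1 v 1 | 26/35 = 74.3% | 32/35 = 91.4% | -17.1 (-34.4 to 0.9) |
| 2 v 1 | 26/34 = 76.5% | 32/35 = 91.4% | -15.0 (-32.4 to 2.8) |
| 3 v 1 | 26/33 = 78.8% | 32/35 = 91.4% | -12.6 (-30.1 to 4.7) |
| 5 v 1 | 26/31 = 83.9% | 32/35 = 91.4% | -7.6 (-25.0 to 8.9) |

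Even timing would give 10 x 2/8 = 2.5 v 4 x 2/8 = 1, so it lies between the 2 v 1 and 3 v 1 rows: a shift of 1.7 to 4.1 points. The 5 v 1 row needs drug-arm stopping to be concentrated before week 2. Every interval includes zero.

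For VAS and efficacy no size can be derived from the documents.

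**The case against.** The strongest reply is that the plan never says early stoppers leave the completion proportion. Section 7.3 states whom the population will include. In section 7.1 the rule follows the target of 30 completers and, in context, widens the analysis beyond completers. Section 3.4 and the Study Summary speak of subjects or patients without limiting them to the 7.3 set. This stands as a limit on certainty: the denominator is inferred. It does not remove the gap, because if 7.3 is not the membership rule, the endpoint has no stated denominator at all.

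A reader might also infer that early intolerance would vanish from the report. The documents do not support that. Under 8.4 to 8.6, adverse events, including those that lead to stopping the drug or leaving the study, are recorded for everyone exposed, and all adverse events are a secondary safety endpoint in 3.4. What remains uncovered is stopping for other reasons, and the completion proportion itself.

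Nor should 5.6, 5.7 and 8.1 be read as removing subjects from the analysis. They govern study participation and replacement, and are silent on how these subjects are counted.

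Finally, the effect may be small. If nobody fails either condition, nothing changes; equal early stopping barely moves the difference; and the plan sets no completion threshold that an inflated rate could pass. All of this stands, and it bears on severity.

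**Conclusion.** The point holds in conditional form. The completion endpoint has no denominator of its own, and the one set the plan defines would, if used, inflate completion in any arm that has both an early stopper and a completer. On the assumed counts the rise is about 5 points with 2 of 7 stopping early and 10 points with 4 of 7. The between-arm difference shrinks by 1.7 to 4.1 points at roughly even timing and by 9.1 points (from -16.7 to -7.6) with 5 v 1.

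A reader might infer that the restricted set would overturn a significance result. No case shown supports that; the estimate moves and the interval still includes zero. This should be fixed rather than must be fixed: a primary endpoint is affected in a known, favourable direction for each arm's proportion, but the denominator is inferred, the size is unknown, and adverse-event stops are captured elsewhere.

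**What to change.** Reword sections 7.1 and 7.3, with cross-references in 5.6, 5.7 and 8.1:

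1. **Completion set.** Analyse completion in all subjects assigned at Day 1 who received at least one dose, by assigned arm. Naming Day 1 and dosing matters because section 5.3 ties allocation to an ID number given at screening, so a set described only as all randomised could take in screen failures.
2. **Non-completer.** Count anyone who permanently stopped study drops before the end of the scheduled eight-week course, for any reason, including subjects excluded or withdrawn under 5.6 and 5.7 or replaced under 8.1. A subject who used the full dispensed supply and attended week 8 within its ±2 day window is not a non-completer merely because the 14-day supply ended before the visit.
3. **VAS and efficacy.** Include all such dosed subjects with any post-baseline value, in their assigned arm, and report missing values by arm and visit.
4. **Two-week set.** Keep it as a supportive analysis.

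No clinical rule, visit or procedure changes. The costs are that the completion rate may look less favourable, and that early stoppers will have no week 8 Rose Bengal or Schirmer value, because the withdrawal visit in 4.4.2 follows the week 10 procedures (6.5.7), which omit both.

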8.1 Adverse Event Definitions

The following are specific definitions of terms guided by the International Conference on Harmonization (ICH) Guidelines for Good Clinical Practice (GCP) and the U.S. Code of Federal Regulations that apply to this section:

Adverse Event: Any untoward medical occurrence in a subject or clinical investigation subject administered a pharmaceutical product and which does not necessarily have to have a causal relationship with this treatment. An adverse event can be any unfavorable sign (including an abnormal laboratory finding), symptom, or disease temporally associated with the use of the investigational product, whether or not considered related to the investigational product.

Subjects will be reminded to inform the study staff of any adverse effects that they have experienced or are experiencing after the first administration of study drug. In addition, subjects will record adverse events in their diary throughout the study. All reports of adverse events during the study will be recorded on an Adverse Event Case Report Form (CRF). The subject should not be prompted about any adverse events that may occur during this trial.

For each adverse event, the following information will be recorded on the subject's Case Report Form(s): onset date, end date or continues, intensity, duration, relationship to test patch, action taken, and outcome. If a subject experiences a serious adverse event (SAE), study staff may discontinue the subject from study participation. The study staff must notify the IRB within 24 hours of receipt of the information. The study staff will instruct the subject to notify the research facility should any adverse

event occur within 7 days of study completion. (For definitions of an AE and SAE, see below). Subjects who withdraw due to an adverse event may be replaced.

- **Serious Adverse Event:** An untoward medical occurrence that at any dose:
 1. results in death
 2. is life-threatening
 3. requires inpatient hospitalization or prolongs existing hospitalization
 4. results in persistent or significant disability/incapacity
 5. is a congenital anomaly/ birth defect
 6. requires medical or surgical intervention to prevent any of the occurrences noted above.

- **Life-threatening:** Any adverse drug experience in which the subject was at risk of death at the time of the event. It does not refer to an event which hypothetically might have caused death if it were more severe.

- **Unexpected adverse event:** Any adverse event, the specificity or severity of which is not consistent with the current Investigator's Brochure.

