5.3 Method for Assigning Subjects to Treatment Groups

This Randomized placebo-controlled trial will have two study groups. Subjects will be randomly assigned to one of two groups (#1, #2). Group #1 will receive placebo (drug vehicle; control group) and Group #2 will receive study drug (rhDNase 0.1%; test group). We will use a computer-based random code generator (Research Randomizer; <http://randomizer.org/>) to generate 1 set of 72 non-unique, unsorted numbers with a range from 1 to 2 representing the group number (#1 is control group, #2 is test group). Each subject will be assigned a study identification (ID) number at screening, eg. subject #1, subject #2, subject #3 and so on. Based on the randomizer generated table, subject #1 will receive either placebo (#1 group) or study drug (#2 group). This will be repeated for each subject. For reproducibility purpose, we will document the final randomization schedule and the random SEED number used to generate the schedule. Randomization will be performed by the Illinois Eye and Ear Infirmary's pharmacy, and neither participants nor research staff will be aware of the assigned treatments. The person conducting the randomization will remain masked as well.

The study identification (ID) number will be used on all study-related documents. To maintain confidentiality, the subject's name will not be recorded on any study document other than the informed consent form. The drug vial number will be linked to the patient identification number.

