8.6 Adverse Event Reporting

All subjects who have been exposed to study drug will be evaluated for adverse events. Adverse events will be recorded starting after the first dose of study drug and continuing until the end of the study. All adverse events will be evaluated beginning with onset, and evaluation will continue until resolution is noted, or until the Investigator determines that the subject's condition is stable, whichever is earlier. The Investigator will take all appropriate and necessary therapeutic measures required for resolution of the adverse event. Any medication necessary for the treatment of an adverse event must be recorded on the concomitant medication case report form. If more than one distinct adverse event occurs, each event should be recorded separately. Procedures such as surgery should not be recorded as adverse events. However, the medical condition for which the procedure was performed should be reported if it meets the definition of adverse event as described previously.

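### Early adverse-event withdrawals fall outside the only analysis set and so out of the primary safety endpoint, and section 8.1 allows them to be replaced without saying how they or their replacements are counted

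*Combined protocol and SAP*

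**What the plan says.** - **Replacement.** Section 8.1: "Subjects who withdraw due to an adverse event may be replaced". The sentence names no decision-maker, limit, allocation rule or analysis rule.
- **Primary safety endpoint.** Section 3.4: "The proportion of subjects at week 8 who were able to successfully complete a full eight weeks of therapy", on four-times-daily dosing. Section 3.4 names no denominator. Section 7.2 promises a 95% confidence interval for drug against placebo on this endpoint.
- **Analysis set.** Section 7.3 defines a single population: enrolled subjects who "received at least two weeks of treatment with study eye drops and attended at least the first post-treatment (week 2) follow up visit". Section 7.1 gives the same rule. No separate safety population is defined for the completion endpoint.
- **Allocation list.** Section 5.3 has the pharmacy "generate 1 set of 72 non-unique, unsorted numbers with a range from 1 to 2 representing the group number". It makes no provision for replacements.
- **Dropout allowance.** Section 7.1: "A total of 72 subjects will be enrolled so that even if 20% of subjects are unable to complete the study", at least 30 per group should still remain.
- **Stops after worsening.** Where rescue anti-inflammatory therapy is started or study drug is stopped, 5.6 describes the subject as excluded from the study and 5.7 as withdrawn from it. Neither says what this means for the analysis.

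**The concern.** Tolerating eight weeks of drops is a primary objective (section 2), and a subject who stops for an adverse event is the failure that the 3.4 endpoint is meant to count. In 8.1 that same failure triggers an optional replacement, after the outcome is known. If the failure is then not counted, the trial reports a completion rate that is too high. If drug causes more early stops than vehicle, the difference between arms shrinks too. A first-in-eye tolerability trial could then make the drops look better tolerated than they are. The question is which provision causes the loss: the replacement sentence, the analysis set, or the two together.

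**Working it through.** **Inputs from the documents.** Target of 30 completers per group (60 in total), 72 enrolled, 20% non-completion (7.1); a list of 72 allocations (5.3); the two-week rule (7.1, 7.3). The documents give no adverse-event withdrawal rate, so the rates below are assumptions.

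**1. The plan's own figure.** 60 × 1.2 = 72, which reproduces the plan. The usual inflation is 60 / (1 − 0.20) = 75. At 20% loss, 72 × 0.80 = 57.6 completers (28.8 per arm); 72 yields 60 completers only if loss is at most 1 − 60/72 = 16.7%. This is a separate issue, but it bears on what giving up replacement would cost.

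**2. One arm under different denominators.** Let *e* be the proportion stopping for an adverse event before meeting the 7.3 rule, *l* the proportion stopping later for an adverse event, and assume no other losses. Take *e* + *l* = 0.20.

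- True completion: 1 − *e* − *l* = 0.80.
- Completion in the 7.3 set: (1 − *e* − *l*) / (1 − *e*).

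| Early / late | True | 7.3 set |
|---|---|---|
| 0% / 20% | 80% | 80.0% |
| 5% / 15% | 80% | 84.2% |
| 10% / 10% | 80% | 88.9% |
| 15% / 5% | 80% | 94.1% |
| 20% / 0% | 80% | 100% |

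**3. Does replacement change this?** Suppose an arm has 36 places and each is refilled until someone does not stop for an adverse event, with replacements having the same chances as everyone else. Expected numbers are 36 / 0.80 = 45 subjects and 36 completers.

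- Everyone dosed kept: 36/45 = 80%, so no shift.
- 7.3 set with the 10% / 10% split: 36 / (45 × 0.90) = 36/40.5 = 88.9%, the same as without replacement.
- Replaced subjects removed altogether: 36/36 = 100%.

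The rise from 80% to 88.9% therefore comes from the two-week rule. The 100% needs a further step, removing replaced subjects, which is written nowhere.

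**4. Between arms.** Assume 20% adverse-event withdrawal on drug and 5% on vehicle, half of each early. The true difference is 80% − 95% = −15 points. In the 7.3 set it is 0.80/0.90 − 0.95/0.975 = 88.9% − 97.4%, about −8.5 points. With early/late splits of 5/15 on drug and 1/4 on vehicle it is −11.7 points; with 15/5 and 4/1 it is −4.8 points.

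**5. A single realised arm.** Take 36 subjects with 4 early and 3 late adverse-event stops.

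- All randomised: 29/36 = 80.6%.
- 7.3 set, no replacement: 29/32 = 90.6%.
- 7.3 set with seven replacements who all happen to complete: 36/39 = 92.3%.
- Replaced subjects dropped: 36/36 = 100%.

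Most of the inflation is there before any replacement. The step from 90.6% to 92.3% reflects the assumption that all seven replacements complete.

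**The case against.** The strongest reply is that the replacement sentence causes no bias by itself. Sections 7.1 and 7.3 define the analysis set without reference to replacement, so a subject who stops after meeting the two-week rule stays in and can be counted as a failure. Section 8.6 adds that "All subjects who have been exposed to study drug will be evaluated for adverse events", so the events themselves are not lost. An allowance for dropout and an option to replace can coexist, and extending a documented, seeded list by further random draws keeps allocation random. All of this stands, and step 3 confirms the arithmetic.

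It does not answer the point about early stops. Section 8.6 governs the recording of events, not the completion denominator, and 7.3 removes early failures with or without replacement. Nor does it settle later stops, because 5.6 can be read as taking such subjects out of the analysis.

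A reader might infer three stronger things:

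- *That replaced subjects leave the denominator, so nearly all intolerance is hidden.* No passage says so.
- *That a replacement inherits the withdrawn subject's arm, so allocation follows outcome.* The documents do not say this. Section 5.3 has no entry for replacements, which is a gap and not a contradiction.
- *That the treatment code could be inferred from supply.* Nothing supports this. The pharmacy randomises and dispenses, and staff are masked (5.3, 5.7). Section 5.7 does let the investigator break a code after a severe event. That would reveal a replacement's treatment only if the arm were inherited, which is not stated.

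**Conclusion.** The concern holds in limited form. As written, the plan overstates completion in any arm with adverse-event stops before the two-week rule is met, because 7.1 and 7.3 take those failures out of the 3.4 endpoint. Section 8.1 adds an optional, outcome-triggered replacement with no rule for allocation or counting, and 5.6 and 5.7 leave the status of later stops open.

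At an assumed 20% adverse-event withdrawal with no other losses, the reported rate runs from 80% (no early stops) to 100% (all early), and is 88.9% at an even split. Under the assumptions of step 4, a 15-point deficit on drug shrinks to between 4.8 and 11.7 points. These figures depend on assumed rates and splits. The direction within an arm does not: removing only failures cannot lower a completion rate.

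**What to change.** 1. In 3.4 and 7.3, state that the primary safety denominator is every randomised subject who received a dose, in the arm originally assigned, and that a subject who stops the drops for an adverse event counts as a non-completer, whether or not replaced. This is the essential change; deleting the 8.1 sentence alone would leave the bias in place.
2. Delete the replacement sentence in 8.1. Alternatively, state that any added subject receives a new random allocation from a list extended in advance, is additional to those already enrolled, never substitutes for anyone and never inherits an arm.
3. Reconcile 5.6 and 5.7 on what exclusion or withdrawal means for the analysis.

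The cost is a few sentences and no new data collection. The reported completion rate may be less favourable. Without replacement there may also be fewer completers: at the plan's own 20% loss, 72 leaves about 57.6 against the stated 60, so the 72 does not fully cover that loss. If 60 completers matter, lengthen the randomisation list before enrolment rather than adding subjects in response to adverse events.
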